9 EFFICACY ANALYSIS

Efficacy analysis will include best overall response (BOR), objective response rate (ORR), clinical benefit rate (CBR), duration of response (DOR), time to response (TTR), [REDACTED]

All tumor response and time to event data will be listed by subject.

9.1 *Best Overall Response*

All lesions, including lymph nodes, will be categorized as target or non-target lesions at baseline and evaluated at each post-baseline tumor assessment to determine the overall response as one of the following: complete response (CR), partial response (PR), stable disease (SD), progressive disease (PD), and not evaluated (NE) based on RECIST 1.1 (E.A. Eisenhauer et al. 2009). The best overall response is determined based on the overall response from each post-baseline tumor assessment in the following order: CR, PR, SD, PD, and NE. For CR and PR, changes in tumor measurements must be confirmed by a repeat assessment at least 4 weeks after the time when criteria for CR or PR are first met. The number and percentage of subjects in each best overall response category will be summarized based on response evaluable population.

9.2 *Objective Response Rate and Clinical Benefit Rate*

ORR is defined as the proportion of subjects who have confirmed CR or PR as their best overall response. CBR is defined as the proportion of subjects who have CR, PR or SD as their best overall response. The number and percentage of subjects who achieve objective response or clinical benefit will be summarized based on response evaluable population. The 95% exact confidence interval using Clopper-Pearson method will be calculated for ORR and CBR. The maximum percentage decrease from baseline in sum of the longest diameter of all target lesions will be plotted for each subject. In addition, BOR and ORR will also be summarized based on all subjects treated.

The immune-related response criteria (irRC) (J.D. Wolchok 2009) may be applied to re-evaluate BOR, ORR, and CBR. The number and percentage of subjects in each category per irRC will be summarized similarly.

All lesion measurements and tumor response assessments will be provided in a listing.

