#### 4.1.3 Tumor Assessments

Tumor response assessments for all subjects will occur every 8 weeks ( $\pm 7$  days) (see Section 9.0). Tumor response will be evaluated using Response Evaluation Criteria in Solid Tumors (RECIST) version 1.1. Subjects with progressive disease (PD) but with otherwise stable or improved performance and clinical status may continue to be treated with study drug in the event of a perceived benefit per Investigator (e.g., non-availability of alternate standard of care therapies). Subjects with a partial response (PR) or stable disease (SD) will continue to receive NKTR-214 until achievement of a confirmed complete response (CR), disease progression, or intolerability to therapy. It is at the discretion of the Investigator to continue treating subjects with a confirmed CR.

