#### 4.1.4 Post-treatment

Subjects who discontinue NKTR-214 due to reasons other than radiographic disease progression will continue radiologic tumor assessments every 3 months until disease progression per RECIST v1.1 or start of subsequent anti-cancer therapy. Subjects will also be contacted for survival every 3 months until death, withdrawal of consent, study termination by the Sponsor, lost to follow-up, or for a maximum of 3 years after Cycle 1 Day 1.

A schematic of the study design is presented in Section 1.1 and the Schedule of Assessments for the Dose Escalation and Dose Expansion cohorts is in Section 1.2.

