### 6.4 Radiographic Assessments

Radiographic assessments (chest/abdomen/pelvis) by computed tomography (CT) scan or magnetic resonance imaging (MRI) are required for all subjects for tumor measurements. CT

scans or MRIs will be performed, target lesions measured, and tumor response evaluation completed at Screening (within 28 days prior to Cycle 1 Day 1) and every 8 weeks ( $\pm 7$  days) from Cycle 1 Day 1 while on study treatment, until PD is noted (even if subject has stopped treatment with study drug) or the subject withdraws consent.

The same method of assessment (CT or MRI) and the same technique for acquisition of images must be used for all study assessments. Baseline imaging should be done at the same institution/facility which will be used to measure response during the subject's participation in the study. Radiographic assessments will also be conducted by an independent central imaging core laboratory for all dose escalation and dose expansion cohorts. There must at least one measurable solid tumor by RECIST version 1.1 present on the Screening scan.

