### 10.5.3 Efficacy

The efficacy outcomes will include:

1. objective response rate (ORR)
2. best overall response (BOR)

■ [REDACTED]

4. duration of response (DOR)

5. clinical benefit rate (CBR)

6. time to response (TTR)

■ [REDACTED]

The primary efficacy measurement will be ORR per RECIST v1.1 based on the Response Evaluable population by tumor type. The number and proportion of subjects with objective tumor response (CR and PR) will be calculated based on number of subjects with measurable disease at baseline. Ninety-five percent (95%) confidence interval (CI) will also be calculated using exact binomial method. Data listing for tumor assessments and tumor response will be provided.

A secondary measurement will be BOR per RECIST v1.1 based on the Response Evaluable population by tumor type. The number and proportion of subjects with a best overall response of CR or PR will be calculated based on number of subjects with measurable disease at baseline. Ninety-five percent (95%) CI will also be calculated using exact binomial method.

DOR will be defined as the time from first documented CR or PR until the earliest evidence of disease progression, new subsequent anti-cancer therapy, or death from any cause. DOR will be estimated using Kaplan-Meier method for those subjects who have a CR or PR.

Clinical benefit rate will be calculated as the number of subjects with confirmed CR, PR, or SD (where the duration of SD should be  $\geq 3$  months) divided by the total number of subjects in the Response Evaluable Population. The number and proportion of subjects with clinical benefit will be summarized.

The time to response will be summarized descriptively for subjects who have a CR or PR.

[REDACTED]

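### SAP 9.1 sets no cut-off at first progression for best overall response, so a confirmed response seen during treatment beyond progression can count in the primary ORR

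*SAP*

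**What the plan says.** **Combining rule.** SAP 9.1 uses RECIST 1.1 to grade each post-baseline scan and then states how the grades are combined: "The best overall response is determined based on the overall response from each post-baseline tumor assessment in the following order", from CR down through PR, SD and PD to NE. For CR and PR, changes in tumour measurements "must be confirmed by a repeat assessment at least 4 weeks after the time when criteria for CR or PR are first met".

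**Endpoints built on it.** In SAP 9.2, "ORR is defined as the proportion of subjects who have confirmed CR or PR as their best overall response", and CBR adds subjects whose best response is SD. Protocol 10.5.3 gives ORR its status: "The primary efficacy measurement will be ORR per RECIST v1.1 based on the Response Evaluable population by tumor type".

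**Treatment and imaging after PD.** Protocol 4.1.3 says: "Subjects with progressive disease (PD) but with otherwise stable or improved performance and clinical status may continue to be treated with study drug". Protocol 6.3 also allows this. The imaging footnotes to the two schedules (Protocol Table 1, note v; Table 2, note u) ask for scans every 8 weeks and at End of Treatment unless one was done within 4 weeks. They set no stop at PD for a subject still on treatment. Protocol 6.4 differs: its 8-weekly scans run "until PD is noted (even if subject has stopped treatment with study drug) or the subject withdraws consent". For subjects who stop treatment without radiographic progression, Protocol 4.1.4 continues imaging "every 3 months until disease progression per RECIST v1.1 or start of subsequent anti-cancer therapy". Protocol 6.5 and the same schedule footnotes agree with 4.1.4.

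**Duration of response.** Protocol 9.2.2.3.2 and SAP 9.4 run DOR from first CR or PR to PD or death. Protocol 10.5.3 also ends it at new anti-cancer therapy.

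**The concern.** The rule in SAP 9.1 has an order of merit but no order in time. PR and SD both rank above PD, so a scan after progression can displace the progression. The protocol keeps some subjects on treatment after PD, so the case can arise.

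ORR is the primary efficacy measure, and BOR, CBR, TTR and DOR depend on the same classification. The error could go in only one direction, because a later scan can raise a subject's best response but never lower it. The trial is open-label. A window left open until analysis could be settled after it is known which subjects responded late.

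**Working it through.** The plan gives no ORR target, power or precision figure, so there is no stated number to reproduce. The check is a reading of the rules against each other, followed by arithmetic for scale.

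**Step 1. Does any visible text close the window?** SAP 9.1, SAP 9.2 and Protocol 10.5.3 do not. The BOR tables (Protocol Table 6; SAP 16.1) have rows starting with CR, PR or NE but none starting with PD. A subject whose PD comes first is therefore left to the ranking in SAP 9.1. The confirmation rule sets a minimum gap of 4 weeks and does not require the response to precede PD. The SAP's censoring table is redacted, but the visible text of SAP 9.4 applies it to DOR and DCB, not to BOR.

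**Step 2. Can a scan after PD be graded PR or SD?** Under Protocol 9.2.2.1, target-lesion PR is at least a 30% fall from the baseline sum, and nothing in that definition bars PR after an earlier PD. SD is judged against the smallest sum on study. After target-lesion PD, the sum would have to drop back inside the limits of a 20% and 5 mm rise over that smallest value.

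**Step 3. Can such scans exist?** Yes, under Protocol 4.1.3, 6.3 and the schedule footnotes. A subject treated for more than 4 weeks past the PD scan is due at least an End-of-Treatment scan. Under Protocol 6.4 taken alone, no. The sections conflict.

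**Step 4. Apply the rule to a sequence.** Take scans at weeks 8, 16 and 24 graded PD, PR, PR.

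- Confirmation: 24 − 16 = 8 weeks, which meets the 4-week minimum.
- BOR by ranking: PR. The subject counts in ORR, with TTR at the week-16 scan.
- DOR starts at week 16, but the first PD is at week 8. Measured to that PD, DOR is 8 − 16 = −8 weeks; otherwise a second PD must be used, which neither document defines.
- With PD at week 8 and SD at week 16, BOR by ranking is SD and the subject counts in the SAP's CBR. SAP 9.2 states no minimum SD duration, whereas Protocol 10.5.3 requires at least 3 months.

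**Step 5. Size.** ORR = x/n. The SAP's Clopper-Pearson 95% limits are the 0.025 quantile of Beta(x, n − x + 1) and the 0.975 quantile of Beta(x + 1, n − x); the lower limit is 0 when x = 0. The n = 50 comes from the planned expansion size; n = 40 is an assumed smaller evaluable set. The base counts and numbers of late responses are assumptions. The 10% base matches the approximate aldesleukin durable-response rate in Protocol 2.1, which is not a planning rate for this trial.

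| n | Responses up to first PD | ORR (95% CI) | Late responses added | ORR (95% CI) |
|---|---|---|---|---|
| 50 | 5 | 10.0% (3.3 to 21.8) | 1 | 12.0% (4.5 to 24.3) |
| 50 | 5 | 10.0% (3.3 to 21.8) | 2 | 14.0% (5.8 to 26.7) |
| 50 | 0 | 0% (0 to 7.1) | 1 | 2.0% (0.1 to 10.6) |
| 50 | 10 | 20.0% (10.0 to 33.7) | 1 | 22.0% (11.5 to 36.0) |
| 40 | 4 | 10.0% (2.8 to 23.7) | 1 | 12.5% (4.2 to 26.8) |

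Each late response adds 1/50 = 2.0 points, or 1/40 = 2.5 points.

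**The case against.** The strongest reply is that the SAP is silent rather than permissive. Time-point grading and the primary measure are both tied to RECIST 1.1. The guideline itself, and the imaging charter mentioned in Protocol 9.0, are not available here and may close the window. The DOR definitions assume that PD follows response. Footnote a to the BOR tables shows that sequence matters: disease that reappears after a true CR is PD even if it meets PR criteria. A programmer could well apply the cut-off unprompted. This stands as a reason not to say that the SAP intends to count late responses. It does not remove the gap, because SAP 9.1 states its own combining rule and that rule, followed literally, gives the result in Step 4.

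Second, a reader might infer that scans after PD will certainly be collected. The documents do not support that: Protocol 6.4 stops at PD, and the 8-weekly interval in Protocol 4.1.3 sets frequency rather than duration. Such scans can exist; how many is unknown. The optional irRC re-evaluation in SAP 9.2 does not settle this either, since what it requires lies in a cited paper that is not available here.

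Third, a reader might infer that responses to a subject's next therapy would enter ORR. That is poorly supported. Protocol 4.1.4, 6.5 and both schedule footnotes stop post-treatment imaging at new therapy, and Protocol 6.15 prohibits other anti-cancer therapy on study apart from limited palliative radiation. Only Protocol 6.4 lacks that stop, and two scans at least 4 weeks apart would be needed.

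Finally, a confirmed PR after PD is a demanding event, and SAP 9.2 lists all measurements and assessments by subject, so any case could be found and recalculated. This limits the likely size but does not justify leaving the primary endpoint's window unstated.

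**Conclusion.** The point holds as a defect in the stated rule: SAP 9.1 does not limit BOR to assessments up to first RECIST 1.1 PD, and treatment beyond PD makes the omission capable of changing the result. Any effect on ORR or CBR is upward, at 2 points of ORR per affected subject with 50 evaluable. This rests on a literal reading of SAP 9.1, on scans being taken after PD as the schedules allow, and on at least one subject then having a confirmed response (for ORR) or an SD scan (for CBR). The documents give no basis for estimating how many.

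It would go too far to conclude that the reported ORR will be inflated, or that an error rate is affected. Protocol 10.1 makes all analyses descriptive, and no ORR hypothesis or threshold is stated, so the effect is on the estimate and its interval. The point is worth correcting before analysis, but it does not undermine the design.

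**What to change.** In SAP 9.1, add a sentence: RECIST 1.1 BOR, and the ORR, CBR, TTR and DOR built on it, use only assessments up to and including the first documented PD and before any subsequent anti-cancer therapy. The second condition is for consistency with the DOR definition in Protocol 10.5.3. Report later responses separately, for example in the irRC tables if that analysis is done.

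Reconcile the imaging end-point in Protocol 6.4 with Protocol 4.1.3, 4.1.4, 6.5 and the imaging footnotes to Tables 1 and 2, so that it is clear whether scans continue on treatment after PD and whether they stop at new therapy.

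The cost is one SAP sentence and a wording alignment in the protocol. ORR and CBR may come out slightly lower than under the literal rule.

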1 INTRODUCTION

This statistical analysis plan (SAP) outlines the statistical methods to be implemented during the analyses of data collected within the scope of Nektar Therapeutics Protocol 15-214-01 [A Phase 1/2, Open-label, Multicenter, Dose Escalation and Dose Expansion Study of NKTR-214 in Subjects with Locally Advanced or Metastatic Solid Tumor Malignancies] dated 24 October 2016. The purpose of this SAP is to provide details on the analyses. Any deviations from the SAP will be documented in the clinical study report (CSR).

Details for pharmacokinetic (PK) methods, parameter calculations, and analyses will be included in a separate pharmacokinetic analysis plan (PKAP) prepared by Nektar Clinical Pharmacology. Nektar Clinical Pharmacology will also identify the subjects who are eligible for inclusion in the PK analysis population.

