9.4 Duration of Response and Clinical Benefit

Duration of response (DOR) is only defined for subjects whose best overall response is CR or PR. The duration of response is the time between the first CR or PR, whichever is earlier, to progressive disease or death, whichever is earlier. DOR is subject to the censoring rules as given in Table 1. DOR will be listed but not summarized unless there is a sufficient number of subjects who achieve ORR. In such case, DOR will be summarized using the Kaplan-Meier method with number and percentage of subjects who have events or censored, the quartiles (25%, median, and 75%) and 95% confidence interval for the median.

Duration of clinical benefit (DCB) is only defined for subjects whose best overall response are CR, PR, or SD. The duration of clinical benefit is the time between the first CR, PR, or SD whichever is earlier, to progressive disease or death, whichever is earlier. DCB is subject to the censoring rules as given in Table 1. DCB will be listed but not summarized unless there is a sufficient number of subjects who achieve ORR. In such case, DCB will be summarized using the Kaplan-Meier method with number and percentage of subjects who have events or censored, the quartiles (25%, median, and 75%) and 95% confidence interval for the median.

[REDACTED]

[REDACTED]

[REDACTED]	[REDACTED]	[REDACTED]
[REDACTED]	[REDACTED]	[REDACTED]
[REDACTED]	[REDACTED]	[REDACTED]
[REDACTED]	[REDACTED]	[REDACTED]

[REDACTED]	[REDACTED]	[REDACTED]
[REDACTED]	[REDACTED]	[REDACTED]
[REDACTED]	[REDACTED]	[REDACTED]
[REDACTED]	[REDACTED]	[REDACTED]
[REDACTED]	[REDACTED]	[REDACTED]

[REDACTED]

[REDACTED]

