14 CHANGES TO PROTOCOL-SPECIFIED ANALYSES

No changes from the protocol specified analyses are planned.

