16 APPENDICES

16.1 Evaluation of Overall Response using RECIST 1.1

Overall response first time point	Overall response subsequent time point	Best overall response
CR	CR	CR
CR	PR	SD, PD, or PR ^a
CR	SD	SD provided minimum criteria for SD duration met, otherwise, PD.
CR	PD	SD provided minimum criteria for SD duration met, otherwise, PD.
CR	NE	SD provided minimum criteria for SD duration met, otherwise, NE.
PR	CR	PR
PR	PR	PR
PR	SD	SD
PR	PD	SD provided minimum criteria for SD duration met, otherwise, PD.
PR	NE	SD provided minimum criteria for SD duration met, otherwise, NE.
NE	NE	NE

Abbreviations CR, complete response; PR, partial response; SD, stable disease, PD; progressive disease; NE, inevaluable.

^a If a CR is truly met at first time point, then any disease seen at a subsequent time point, even disease meeting PR criteria relative to baseline, makes the disease PD at that point (since disease must have reappeared after CR). Best response would depend on whether minimum duration for SD was met. However, sometimes 'CR' may be claimed when subsequent scans suggest small lesions were likely still present and in fact the subject had PR, not CR at the first time point. Under these circumstances, the original CR should be changed to PR and the best response is PR. Source: Eisenhauer, 2009

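### The SAP counts any best response of stable disease as clinical benefit, the protocol requires at least 3 months, and neither says how that duration is timed for the rate

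*SAP*

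**What the plan says.** CBR is a secondary efficacy endpoint in both documents.

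- **Protocol 10.5.3:** "Clinical benefit rate will be calculated as the number of subjects with confirmed CR, PR, or SD (where the duration of SD should be" at least 3 months), divided by the Response Evaluable Population.
- **SAP 9.2:** "CBR is defined as the proportion of subjects who have CR, PR or SD as their best overall response", with an exact 95% interval. No duration is attached to SD.
- **SAP 9.1:** best overall response is the best category over the post-baseline scans, "in the following order: CR, PR, SD, PD, and NE". CR and PR need confirmation; SD has no minimum.
- **SAP Appendix 16.1:** some sequences resolve to "SD provided minimum criteria for SD duration met, otherwise, PD". No number of weeks and no starting point are given.
- **SAP 9.4**, for a different endpoint: "The duration of clinical benefit is the time between the first CR, PR, or SD whichever is earlier", ending at progression or death.
- **Protocol 6.4:** scans every 8 weeks, plus or minus 7 days, "from Cycle 1 Day 1 while on study treatment, until PD is noted".
- **SAP 14:** "No changes from the protocol specified analyses are planned". SAP 1 ties the plan to a protocol "dated 24 October 2016".

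**The concern.** Two different rates carry one name. The protocol's rate requires disease control that lasts. The SAP's rate is met by a single scan showing SD about 8 weeks after the first dose. Because SAP 14 declares no change, a reader of the study report would take the SAP figure for the protocol's 3-month rate.

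Restoring the words about 3 months would not be enough. Neither CBR definition says whether SD runs from first dose or from the first SD scan, or whether it ends at progression or at the last scan without progression. With scans 8 weeks apart, that choice decides whether a whole group of subjects counts.

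In a single-arm trial the rate and its interval are read at face value, with no control arm to absorb a lenient definition.

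**Working it through.** The documents give no expected CBR, SD rate or progression time, so there is no planned figure to reproduce. The check compares the definitions, then the scan calendar, then the possible size.

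**1. Does anything else in the SAP restore the 3 months?** SAP 9.1 sets no SD minimum. Appendix 16.1 mentions one without a number. It does so only for sequences that begin with CR or PR, has no row that begins with SD, and resolves PR followed by SD to SD without condition. The visible text does not restore it.

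**2. Direction.** Every subject who counts under the protocol also counts under the SAP, but not the reverse. On a common denominator n, with S the number of subjects whose best response is SD lasting under 3 months:

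SAP CBR − protocol CBR = S/n ≥ 0

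At n = 50 (the approximate size of the expansion phase) each such subject adds 1/50 = 2 percentage points.

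**3. Scan calendar.** Scan k falls on day 56k ± 7: days 49–63, 105–119 and 161–175. Three months is about 91 days.

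| How SD is timed | SD at week 8, PD at week 16 | SD at weeks 8 and 16, PD at week 24 |
|---|---|---|
| A. First dose to PD date | 105–119 days, passes | 161–175 days, passes |
| B. First dose to last scan without PD | 49–63 days, fails | 105–119 days, passes |
| C. First SD to PD (the SAP 9.4 clock) | 105−63 = 42 to 119−49 = 70 days, fails | 161−63 = 98 to 175−49 = 126 days, passes |

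The results are the same with 3 months taken as 84, 90, 91.3 or 92 days. The SAP counts both subjects in every row. A subject with SD at the first scan who dies before about day 91 counts under the SAP and fails under all three clocks.

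**4. Possible size (assumptions, not document figures).** Exponential progression, S(t) = exp(−ln2 · t/median), with a month of 30.44 days. Under clocks B and C, with nobody lost between scans, the gap is S(56 d) − S(112 d):

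| Median (months) | Progression-free at day 56 | At day 112 | Gap (points) |
|---|---|---|---|
| 3 | 65.4% | 42.7% | 22.6 |
| 4 | 72.7% | 52.9% | 19.8 |
| 5 | 77.5% | 60.0% | 17.4 |
| 6 | 80.9% | 65.4% | 15.5 |
| 8 | 85.3% | 72.7% | 12.6 |

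(Gaps are taken before rounding.) In 50 subjects that is about 6 to 11.

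Under clock A the gap is 0 if nobody dies, progresses off schedule or is lost between scans. By simulation (400,000 subjects per scenario, medians 3, 4, 6 and 8 months, uniform scan windows), if 2% to 5% a month do, it is about 1.5 to 5.0 points among subjects who reach a first scan, or 1.4 to 4.5 points of all simulated subjects.

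**5. Illustration for B or C at a median of 5 months.** 0.775 × 50 ≈ 39 and 0.600 × 50 = 30. SAP: 39/50 = 78% (Clopper-Pearson 95% CI 64.0 to 88.5). Protocol: 30/50 = 60% (45.2 to 73.6).

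**6. A related mismatch in duration of response (DOR).** Protocol 10.5.3 ends DOR at progression, new anti-cancer therapy or death. Protocol 9.2.2.3.2 ends it at progression or death, and SAP 9.4 follows the latter. The SAP's censoring Table 1 is not visible, so its handling of new therapy cannot be judged.

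**The case against.** Several points on the other side have force.

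- **The direction needs a common denominator.** The two Response Evaluable Populations differ: protocol 10.4 keeps subjects withdrawn for progression or death before a first assessment, while SAP 7 drops them and requires that all eligibility criteria were met. With assumed counts, dropping two ineligible subjects who had benefit turns 15/50 = 30.0% into 13/48 = 27.1%, below the protocol rate. This stands, which is why the claim is limited to the same subjects.
- **SAP 9.4 does supply a clock.** It is the nearest convention, but it is written for duration of clinical benefit and not linked to CBR. Some nearby text is redacted, so the claim about timing covers the visible text only.
- **Appendix 16.1 might have meant 3 months.** That would close the gap only for an unconfirmed CR or PR, not for subjects whose first response is SD.
- **The sizes are modelled.** They are. For B and C the model also treats everyone who progresses between weeks 8 and 16 as SD. A PR at week 8, confirmed at least 4 weeks later and progressing by week 16, counts under both rules, so in that respect the figures are upper bounds. Losses between scans would push them up.
- **The protocol version cannot be matched.** The supplied protocol's title pages were removed. The mismatch between the supplied texts is certain; whether it exists against the version the SAP names needs a check.
- **The stakes are modest.** Analyses are descriptive, and the subject listings would let a 3-month rate be derived later. That limits the severity but does not make the SAP's definition the protocol's.

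**Conclusion.** The concern holds. SAP 9.2 changes the definition of a named secondary endpoint without declaring it, and a CBR produced under it cannot be read as the protocol's 3-month rate. On the same subjects the error goes one way: the SAP rate is equal or higher.

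The true gap is unknown and may be zero. Under the assumptions above it is 0 to about 5 points with clock A, and 12.6 to 22.6 points with clocks B or C. The clock therefore matters as much as the missing 3 months. The definitional conflict and the day ranges follow from the documents; the percentage-point ranges rest on assumed progression and loss rates.

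No decision rule uses CBR, so this should be corrected but does not threaten the trial's conclusions on safety, the MTD or response rate. The DOR inconsistency is separate and also real within the protocol.

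**What to change.** In SAP 9.2, define CBR as the proportion of the Response Evaluable Population with confirmed CR, confirmed PR, or SD of at least 3 months, and state the start and end points that time SD. One option is first dose to last assessment without progression, in which case the week-16 scan is the first scheduled scan that can satisfy it. The SAP 9.4 clock is another. The choice is the sponsor's, but it must be written down.

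Alternatively, keep the SAP definition, declare it in SAP 14, and report the protocol-defined rate beside it.

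Do not put the 3-month figure into Appendix 16.1: it would reclassify some unconfirmed responses and so change best overall response. Check the wording against the protocol version named in SAP 1.

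Separately, reconcile protocol 9.2.2.3.2 and 10.5.3 to one DOR event definition, consistent with SAP 9.4 and its Table 1.

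The cost is wording only: a sentence and a timing rule in SAP 9.2 (or an entry in SAP 14), and one sentence in the protocol for DOR. On the same subjects, CBR under the protocol definition will be equal to or lower than under the current SAP text.

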Statistical Methods:	Safety: The primary safety analyses will include incidence of DLTs by dose cohort. Safety analyses will summarize the incidence, grade and duration of toxicities according to the National Cancer Institute Common Terminology Criteria for AEs (NCI-CTCAE), version 4.03. All AEs will be listed and tabulated by system organ class, preferred term, and coded according to the Medical Dictionary for Regulatory Activities

	
(MedDRA). The incidence of AEs will be tabulated and reviewed for potential significance and clinical importance. Vital signs (including change in weight) and clinical laboratory test results will be listed and summarized descriptively by dose (for the dose escalation phase) and by tumor type (for the dose expansion phase). Any significant physical examination findings will be listed. ECG data will be evaluated by central review. Abnormalities, if present, will be listed. A separate listing and summary of all immune-related AEs (irAEs) will be provided.
 
Efficacy:
 
Efficacy assessments will be summarized separately for the dose escalation and dose expansion cohorts. In order to assess preliminary efficacy, the primary efficacy outcome measurement ORR, and the secondary efficacy outcomes, BOR, CBR, and TTR, will be tabulated by dose and tumor type. [REDACTED]
 
[REDACTED] Individual tumor measurements, tumor size and percent changes in tumor size will be listed. Changes in tumor size will be presented graphically for each specific tumor type. ORR and BOR will each be estimated based on the response evaluable population which is defined as subjects with measurable disease at baseline who receive the study drug and also have one post-baseline assessment of tumor response or are withdrawn due to progressive disease/death prior to first response assessment. DOR will be estimated for subjects who achieve complete response (CR) or partial response (PR). Other secondary efficacy analyses will be based on the all treated population and may be done for the response evaluable population as sensitivity analyses.
 
Pharmacokinetic parameters will be tabulated and summarized with descriptive statistics by dose level. Values for biomarker expression will be calculated at each observation time. Changes in expression from screening to each observation time will be assessed.

--	---

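### The clinical benefit rate has conflicting denominators: all treated subjects by the protocol synopsis, Response Evaluable subjects in protocol 10.5.3 and SAP 9.2, with no labelled all-treated rate planned

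*SAP*

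**What the plan says.** **Protocol synopsis, Statistical Methods.** The Response Evaluable population is assigned to two endpoints: "ORR and BOR will each be estimated based on the response evaluable population". A later sentence covers the rest: "Other secondary efficacy analyses will be based on the all treated population and may be done for the response evaluable population as sensitivity analyses". The same section names CBR among the secondary outcomes: "the secondary efficacy outcomes, BOR, CBR, and TTR, will be tabulated by dose and tumor type". By the synopsis, CBR therefore belongs on all treated subjects, and a Response Evaluable version is optional.

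**Protocol 10.5.3.** CBR is the number of subjects with benefit "divided by the total number of subjects in the Response Evaluable Population".

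**SAP 9.2.** The Response Evaluable population is used for both ORR and CBR: "The number and percentage of subjects who achieve objective response or clinical benefit will be summarized based on response evaluable population". The supplementary summary then reads: "In addition, BOR and ORR will also be summarized based on all subjects treated". CBR is not in it.

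**SAP 14.** The SAP declares no departures from the protocol's analyses.

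**Definitions of the Response Evaluable population.** Protocol 10.4 and the synopsis keep subjects who were withdrawn for progression or death before their first response assessment. SAP 7 has no such clause: it requires at least one post-baseline assessment, and it adds a condition that the subject satisfied every eligibility criterion.

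**The concern.** CBR measures disease control. A subject who leaves before any post-baseline assessment adds nothing to the numerator under either document. Whether that subject stays in the denominator therefore changes the reported rate directly. As the text stands, a programmer following the SAP and a reader following the synopsis would expect different rates from the same data, and SAP 14 gives no sign that a choice was made between them.

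The study is open-label, and Part 2 is a single cohort of about 50 subjects with RCC who are not replaced if they drop out. An unresolved denominator leaves room to choose after the results are known. What is at stake is how a secondary rate is read. No error rate or decision depends on it.

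**Working it through.** The documents state no expected CBR, no target and no drop-out rate, so there is no figure of the plan's own to reproduce. The check compares three denominators.

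**Inputs from the documents.** N = 50 treated, the approximate Part 2 enrolment (protocol 10.2, SAP 4). No replacement in expansion (protocol 10.3). Exact Clopper-Pearson 95% intervals, the SAP 9.2 method.

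**Assumptions, not in the documents.** Between 2 and 10 of the 50 have no post-baseline assessment, 50% to about 63% of them because of progression or death. In the illustration, x = 25 subjects have benefit.

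**Formulas.** Let u be the number unassessed and d the number of those withdrawn for progression or death. Unassessed subjects cannot be CR, PR or SD, so x is the same in every row. Setting the SAP's eligibility condition aside for the moment:

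- All treated: x / N
- Protocol 10.4 set: x / (N − (u − d)), which is N / (N − u + d) times the all-treated rate
- SAP 7 set: x / (N − u), which is N / (N − u) times the all-treated rate

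**Results.** The all-treated rate is 25/50 = 50.0% (35.5–64.5) in every row.

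| u (d) | Protocol 10.4 set | Ratio to all treated | SAP 7 set | Ratio to all treated |
|---|---|---|---|---|
| 2 (1) | 25/49 = 51.0% (36.3–65.6) | 1.02 | 25/48 = 52.1% (37.2–66.7) | 1.04 |
| 5 (3) | 25/48 = 52.1% (37.2–66.7) | 1.04 | 25/45 = 55.6% (40.0–70.4) | 1.11 |
| 8 (5) | 25/47 = 53.2% (38.1–67.9) | 1.06 | 25/42 = 59.5% (43.3–74.4) | 1.19 |
| 10 (6) | 25/46 = 54.3% (39.0–69.1) | 1.09 | 25/40 = 62.5% (45.8–77.3) | 1.25 |

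The ratios do not depend on x. In the last row, 62.5 − 54.3 = 8.2 of the 12.5-point gap between the SAP and all-treated rates comes from the SAP dropping early progression and death. The rest comes from excluding the other unassessed subjects.

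**Effect of the SAP's eligibility condition.** This can move CBR in either direction. Start from 25/50 with 2 unassessed, which gives 25/48 = 52.1%. Removing 3 ineligible subjects who benefited gives (25 − 3)/(48 − 3) = 22/45 = 48.9%, below the all-treated 50.0%. Removing 3 ineligible subjects without benefit gives 25/45 = 55.6%.

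**Limiting case.** With nobody unassessed and nobody ineligible, all three rates agree.

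**The case against.** Several points on the other side have force.

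- **The synopsis does not name CBR in its population sentence.** CBR is caught by a residual phrase, and nearby text is redacted. The two places that name the CBR denominator agree with each other. This stands as a limit on how explicit the conflict is. But the synopsis does list CBR as secondary and leaves it out of the Response Evaluable sentence, so the ordinary reading is all treated.
- **A reader might infer that an all-treated CBR would be unobtainable.** The documents do not support that. SAP 9.1 tabulates BOR by category, SAP 9.2 adds a BOR summary on all treated subjects, and the SAP defines CBR as CR, PR or SD as best response. The point estimate is the sum of three planned rows. What is missing is the labelled result and its interval.
- **A reader might infer that the protocol and the SAP both discard early failures.** Only SAP 7 does. Protocol 10.4 keeps early progression and death as non-benefit, so under 10.5.3 the exclusions are limited to other early losses, such as toxicity or withdrawn consent. For those subjects the true disease status is unknown, not shown to be failure.
- **The upper end of the range may be unrealistic.** The first scheduled on-treatment scan is at 8 weeks. Entry requires life expectancy above 12 weeks and ECOG 0 to 1. An end-of-treatment scan is required unless one was done within 4 weeks, and subjects who stop without progression continue imaging. Ten unassessed of 50 is an assumed high case; 2 to 5 gives a SAP ratio of 1.04 to 1.11.
- **CBR is secondary and all analyses are descriptive** (protocol 10.1). That is correct, and it limits the seriousness of the point.

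**Conclusion.** The denominator conflict is real and lies in current text: all treated by the synopsis, Response Evaluable by protocol 10.5.3 and SAP 9.2, with CBR absent from the SAP's all-treated summary and no departure recorded in SAP 14. Excluding unassessed subjects can only raise CBR. On the stated assumptions (50 treated, 2 to 10 unassessed), the factor is 1.04 to 1.25 under SAP 7 and 1.02 to 1.09 under protocol 10.4. The true size depends on a drop-out count that the documents do not give.

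It would go too far to say that the SAP's CBR must be biased upward, because the eligibility condition can also remove subjects who benefited. Nor is any test, sample size or decision rule affected. The point should be settled before results are tabulated, but it does not threaten the study's main conclusions.

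**What to change.** 1. In protocol 10.5.3 and SAP 9.2, make all treated subjects the CBR denominator, as the synopsis does. State that treated subjects without a post-baseline assessment count as no benefit; the synopsis does not say this, so it needs adding. All treated is not among the named analysis sets, so define it, for example by reference to the Safety Population (at least one full or partial dose).
2. Add CBR with its exact 95% interval to the SAP's all-treated summary.
3. Report the Response Evaluable CBR as a sensitivity analysis, using the protocol 10.4 definition that keeps early progression and death.
4. If the sponsor prefers another denominator, record the departure from the synopsis in SAP 14.

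While editing, settle a separate mismatch in the numerator: protocol 10.5.3 counts stable disease only if it lasts at least 3 months, and SAP 9.2 sets no duration. Aligning the denominator alone would leave two versions of CBR.

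The cost is wording in two sections and one table row. The stated CBR may be lower.
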